2.3.2 KNOWN POTENTIAL BENEFITS

The potential benefits of this study are: The drug could potentially slow, halt or reverse the progression of the neurological abnormalities in MSA, although this is unproven. These include difficulties with speech, walking and autonomic function. There is also the possibility that the drug may be ineffective.

2.3.3 ASSESSMENT OF POTENTIAL RISKS AND BENEFITS

Given the rapidly progressive and fatal nature of multiple system atrophy, there is an urgent need for therapies that can halt or slow the progression of the disease. Thus, performing well-designed clinical trials with medications that have the potential of modifying the natural history of multiple system atrophy is a research priority. Because sirolimus is an FDA-approved medication with a well-known side effects profile, the potential benefits for patients outweigh the potential risks of the study drug.

3 OBJECTIVES AND ENDPOINTS

OBJECTIVES	ENDPOINTS	JUSTIFICATION FOR ENDPOINTS
Primary		

To determine if oral sirolimus is of sufficient promise or futile to slow disease progression in patients with MSA
	
Primary endpoint: Change from baseline to 48 weeks in United Multiple System Atrophy Rating Score (UMSARS) total score in patients taking sirolimus compared with described progression rates in historical controls. We will assume that patients receiving sirolimus will have a change of 4 points less than those reported in natural history studies (see statistical section).
 
Secondary endpoints: Change from baseline to 48 weeks in United Multiple System Atrophy Rating Score (UMSARS) subscores (UMSARS-1 and UMSARS-2) in patients taking sirolimus compared with described progression rates in historical controls. We will assume that patients receiving sirolimus will have a change of 2.5 points less than those reported in natural history studies (see statistical section).
	
UMSARS is a patient-reported, semi-quantitative, validated, disease-specific scale representing the diverse signs and symptoms in MSA (36). The UMSARS is the only validated investigator-administered rating scale to reliably measure semi-quantitatively symptoms and signs in MSA. The instrument has high inter-rater reliability, and internal consistency, for instance the UMSARS-1 has a Cronbach’s alpha of 0.84 and the UMSARS-2 of 0.90 (36). The instrument is sensitive in measuring disease progression (37). It has an Activities of Daily Living score (UMSARS-1, 12 questions) that evaluates motor including autonomic activities and the Motor Examination score (UMSARS-2, 14 questions). UMSARS-3 measures supine/standing BP and UMSARS-4 is a disability scale (1-5). Higher scores on the UMSARS scales mean poorer health.

Secondary		

To assess the potential effects of sirolimus on brain neuroimaging and retinal biomarkers in patients with MSA
	
Brain magnetic resonance changes using dedicated algorithms to evaluate rate of change in diffusivity of defined areas of brain from baseline to 48 weeks in patients receiving sirolimus compared to the progression of putaminal diffusivity reported in longitudinal studies of MSA.
	
Increased putaminal diffusivity has been consistently reported, even in early disease stages of MSA (42, 55-59). Increase in putaminal diffusivity has been reported to be a sensitive neuroimaging measures of disease progression in patients with MSA and has been used previously as neuroimaging

OBJECTIVES	ENDPOINTS	JUSTIFICATION FOR ENDPOINTS
	
Changes in retinal nerve fiber layer (RNFL) using optical coherence tomography from baseline to 48 weeks in patients receiving sirolimus compared to the rate of progression in longitudinal studies of MSA.
	
outcome measure in previous clinical trials of MSA (41, 42).
 
The use of optical coherence tomography (OCT) is emerging as a non-invasive fast technique to measure the thickness of the retinal layers. Even though patients with MSA only rarely have visual complaints, recent studies by our group using OCT showed that the retina of patients with MSA have consistent atrophy of the peripapillary retinal nerve fiber layer (RNFL) and to a lesser extent the macular ganglion cell layer (GCL) complex (13). These abnormalities are progressive overtime and have been recently confirmed by pathological examination in the retinas from three patients with MSA (12, 14).

Tertiary/Exploratory		

To explore the effects of sirolimus on blood biomarkers (exosomal alpha-synuclein particles) in patients with MSA
	
Change from baseline to week-48 in exosomal alpha-synuclein particle concentration in plasma in patients taking sirolimus versus the placebo group
	
The concentration of exosomal alpha-synuclein particles in plasma has been proposed as a biomarker of diagnosis of synucleinopathies. We hypothesize that sirolimus will increase autophagy and, therefore, the degradation of these exosomal alpha-synuclein particles.

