Endpoints:	
Primary Endpoint: Change from baseline to 48 weeks (or last available date) in United Multiple System Atrophy Rating Score (UMSARS) total score compared with described progression rates in historical controls. We will assume that patients receiving sirolimus will have a change of 4 points less than those reported in natural history studies (see statistical section).
 
Secondary Endpoints:
 
 1. Change from baseline to 48 weeks (or last available date) in UMSARS-2 subscale score. We will assume that patients receiving sirolimus will have a change of 2 points less than those reported in historical controls. 2. Change from baseline to 48 weeks (or last available date) in UMSARS-1 subscale score. We will assume that patients receiving sirolimus will have a change of 2 points less than those reported in historical controls. 3. Magnetic resonance changes using dedicated algorithms to evaluate rate of change in diffusivity of defined areas of brain from baseline to 48 weeks. 4. Changes in retinal nerve fiber layer using optical coherence tomography from baseline to 48 weeks. 
Exploratory outcome
 
 1. Change in plasma biomarkers (exosomal alpha-synuclein particle concentration) from baseline to 48 months.

Study Population:	A total of 56 patients with multiple system atrophy will be randomized (42 to active agent and 14 to placebo)

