The UMSARS is a scale that comprises 4 parts. UMSARS-1 scores symptoms of neurological and autonomic dysfunction. UMSARS-2 is a motor examination. UMSARS-3 is a cardiovascular autonomic examination; and UMSARS-4, a global disability scale (36). The UMSARS is the only validated investigator-administered rating scale to reliably measure semi-quantitatively symptoms and signs in MSA. The instrument has high inter-rater reliability, and internal consistency, for instance the UMSARS-1 has a Cronbach's alpha of 0.84 and the UMSARS-2 of 0.90 (36). The instrument is sensitive in measuring disease progression (37). In a study to assess rates of disease progression in MSA and validating UMSARS for sensitivity to change over time, MSA patients were assessed at two time points 12 months apart using the UMSARS 1-4. Fifty patients were assessed twice with an interval of 12.3 months. UMSARS-2 scores progressed by 57.3% ($P < 0.0001$) and the UMSARS-1 scores by 35.6% ($P < 0.0001$) in relation to the respective baseline scores with no differences between motor subtypes, diagnostic categories and gender (37). More recently, the minimally clinically important difference (MCID) for the UMSARS scores were determined (38): the MCID for the UMSARS-1 and the UMSARS-2 was 1.5 points, whereas it was of 3.5 points for the UMSARS total score (UMSARS-1 + UMSARS-2). Already completed natural history studies of MSA (8, 39) have reported the annual rates of change of UMSARS. This has also been reported in the placebo group of a previous clinical trial with rifampicin for MSA (40). These developments are relevant because appreciation of the MCID as well as the described annual changes in UMSARS are crucial for statistically significant effects and power analysis calculation (see statistical section).

The rate of progression of objective markers in MSA has been reported in longitudinal studies measuring the thickness of the retinal nerve fiber layer using retinal OCT (12-14), as well as in studies measuring changes in diffusion to water molecules in the pons and the putamen with specific sequences of brain MRI (41, 42). These markers have been specifically measured at baseline and after 12 months, are able to detect change, correlate with disease progression, and appear to be good candidates to be used as objective outcome measures in clinical trials of MSA.

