9.4.2 ANALYSIS OF THE PRIMARY EFFICACY ENDPOINT

The primary outcome endpoint (UMSARS total score) will be analyzed by comparing the mean decline in total UMSARS score in the active sirolimus group (UMSARS total score at week 48 minus UMSARS total score at baseline) with the pre-specified fixed value of 8.6 (SD: 9.2) using a one-sample t-test. If the difference between the fixed value of 8.6 minus the UMSARS total score in the active sirolimus group is 4 or less, the null hypothesis will be rejected, indicating futility.

Missing data will be addressed by using a regression-based multiple imputation model (78)

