9.4.3 ANALYSIS OF THE SECONDARY ENDPOINT

In order to maintain the overall type I error at the 0.05 level, an hierarchy will be employed as follows: If the primary endpoint is found to be significant at a significance level of 0.05, then the first key secondary endpoint will be tested; if this endpoint is found to be significant in a significance level of 0.05, then the second key secondary endpoint will be tested and so on. The key secondary endpoints and their order in the hierarchy are:

UMSARS sub-scores: The secondary outcome endpoint (UMSARS-1 and UMSARS-2 scores) will be analyzed by comparing the mean decline in total UMSARS-1 and UMSARS-2 score in the active sirolimus group (UMSARS-1 and UMSARS-2 at week 48 minus UMSARS-1 and UMSARS-2 at baseline) with the pre-specified fixed value of 4.5 (SD: 5.5) in each score using a one-sample t-test.

Brain magnetic resonance imaging: The secondary outcome endpoint (putaminal diffusivity) will be analyzed by comparing the mean increase in Trace(D) score in the active sirolimus group (Trace(D) score at week 48 minus Trace(D) score at baseline) with the pre-specified fixed value of 0.07 ($\times 10^{-3}$ mm²/sec) using a one-sample t-test.

Retinal optical coherence tomography: The secondary outcome endpoint (retinal nerve fiber layer

thickness) will be analyzed by comparing the mean decline in RNFL thickness in the active sirolimus group (RNFL at baseline minus RNFL at week 48) with the pre-specified fixed value of 3.7 μm using a one-sample t-test.

Concentration of exosomal αSyn particles: This exploratory outcome endpoint will be analyzed by comparing the mean change in αSyn exosomal particles concentration (week 48 minus baseline) in the active sirolimus group with the placebo group.

In all cases missing data will be addressed by using a regression-based multiple imputation model (78)

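### The UMSARS-1 and UMSARS-2 futility margin is 2 points in the synopsis and 2.5 in Section 3, the statistical section fixes neither, and the hierarchy does not say how the two subscales share its first step

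*Combined protocol and SAP*

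**What the plan says.** **Margins.** In the synopsis (Section 1.1) the entries for UMSARS-2 and UMSARS-1 each carry the sentence "We will assume that patients receiving sirolimus will have a change of 2 points less than those reported in historical controls". Section 3 covers the same two subscores in one entry and assumes "a change of 2.5 points less than those reported in natural history studies", pointing to the statistical section. For the total score, Section 3 assumes "a change of 4 points less than those reported in natural history studies".

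**Statistical section.** Section 9.1 sets out hypotheses for the total score, MRI, OCT and exosomes, but none for either subscale. Section 9.4.3 compares the mean subscale changes "with the pre-specified fixed value of 4.5 (SD: 5.5) in each score using a one-sample t-test". It states no margin and no source for 4.5. For the primary, Section 9.4.2 compares the mean change "with the pre-specified fixed value of 8.6 (SD: 9.2) using a one-sample t-test" and then applies the 4-point margin.

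**Link between the scores.** Section 2.2 describes the "UMSARS total score (UMSARS-1 + UMSARS-2"), that is, the sum of the two parts.

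**Hierarchy.** Section 9.4.3 aims to hold the overall type I error at 0.05 by testing in sequence after the primary. It introduces its list with "The key secondary endpoints and their order in the hierarchy are". The first entry covers both subscales. It gives no order between them and does not say whether one or both must be significant before MRI is tested.

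**The concern.** In this design the null hypothesis is that the drug achieves the stated benefit, and rejection means futility. The margin therefore sets the decision threshold: benchmark minus margin. Two margins for the same endpoints give two thresholds, and the section meant to settle the matter gives a third number with no margin. The choice could then be made after the data are seen, and the same data could support either conclusion.

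The figures also bear on the primary's. If the total is the sum of its parts and all benchmarks come from the same patients, the subscale benchmarks should add to the total benchmark. Margins that share out the total's margin should add to it.

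The shared first step matters because the plan claims error control. Two 0.05 tests on one step keep that claim only under a suitable rule for moving on, and none is given.

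**Working it through.** **Inputs.** Subscale margins 2 (Section 1.1) and 2.5 (Section 3); total margin 4 (Section 3); subscale benchmark 4.5, SD 5.5 (Section 9.4.3); total benchmark 8.6, SD 9.2 (Section 9.4.2); historical sources n=96, mean 7.5, and n=50, mean 10.8 (Section 9.2); 38 evaluable active patients and one-sided alpha 0.05 (Section 9.2). The alpha and sidedness are stated for the primary and assumed here for the subscales.

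**1. The plan's total benchmark reproduces.** (96×7.5 + 50×10.8)/146 = 1260/146 = 8.63, stated as 8.6. Section 9.2 gives only total-score changes for these sources, so 4.5 cannot be checked in the same way.

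**2. Additivity.**
- Benchmarks: 4.5 + 4.5 = 9.0 against 8.6, a gap of 0.4.
- Margins: 2 + 2 = 4, equal to the total's 4; 2.5 + 2.5 = 5, not equal.
- Thresholds: the total's is 8.6 − 4 = 4.6. The subscales give 2×(4.5 − 2) = 5.0 or 2×(4.5 − 2.5) = 4.0, and neither matches. An equal split of 8.6 (assumed) with margin 2 gives 2×(4.3 − 2) = 4.6, which does.

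**3. Observed mean that declares futility.** Cut-off = threshold + t(0.95, 37) × 5.5/√38 = threshold + 1.687 × 0.892 = threshold + 1.51.

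| Reading | Threshold | Cut-off | Chance of declaring futility if the true mean is 4.5 |
|---|---|---|---|
| Section 3, margin 2.5 | 2.0 | 3.51 | 0.87 |
| Synopsis, margin 2 | 2.5 | 4.01 | 0.71 |
| Section 9.4.3 read literally | 4.5 | 6.01 | 0.05 |

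The first two chances come from the noncentral t distribution (n=38, SD 5.5, distance 2.5 or 2). The third is the test's own level. An observed mean of 3.8 is futile under Section 3 and not under the synopsis. A mean of 5 is futile under either margin and not under the literal reading.

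**4. Error at the shared step.** If either subscale may open the next step and the tests are taken alone, the chance of at least one false rejection is 1 − 0.95² = 0.0975 at correlation 0. It is 0.091 at 0.4 and 0.080 at 0.7. The stated SDs imply about 0.4 if they come from one population: (9.2² − 2×5.5²)/(2×5.5²) = 24.14/60.5 = 0.40.

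The subscales are tested only after the primary null (total at most 4.6) is rejected. I simulated the primary and both subscale tests together (n=38, SD 5.5, correlations 0, 0.4 and 0.7, 200,000 trials each), with both subscale means at their null limits. The chance of rejecting the primary and at least one subscale was:
- threshold 2.0: about 0.02;
- threshold 2.5: about 0.05 to 0.06;
- threshold 2.3 (the equal-split example): about 0.04 to 0.05;
- threshold 4.5: about 0.08 to 0.097.

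These figures take both subscale nulls as true. If the primary and one subscale are clearly rejected, while the other subscale null and the MRI null are true, an either rule tests both true nulls at 0.05. The error is then about 1 − 0.95² = 0.0975, taking those two tests as independent. Requiring both subscales, or testing them in order, avoids this.

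**The case against.** Several counter-arguments have force.

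- **The literal 4.5 is probably a drafting omission.** Section 9.4.2 uses the same fixed-value wording and then applies the margin, and Section 9.4.3 leaves out the MRI and OCT margins too. This stands: 2.5 and 2.0 are the serious candidates. But the MRI and OCT margins can be recovered from Section 9.1, and the subscale margin cannot.
- **9.0 against 8.6 is not a demonstrated arithmetic error.** Means must add only within one population. Section 9.4.3 does not say that 4.5 comes from the two sources behind 8.6, the plan cites another natural history study as well, and 0.4 could be rounding. This also stands. What can be said is that 4.5 has no stated source and does not fit 8.6 if the patients are the same.
- **Error inflation is not established.** A reader might infer that the plan's error rate is 0.08 to 0.097. That ignores the requirement to reject the primary first, and it presumes an either rule that the plan does not state. With both subscale nulls true, the range arises only with thresholds at 4.5. The defect is the missing rule.
- **The synopsis numbering is not a testing order.** A reader might see a conflict because the synopsis lists UMSARS-2 first. It numbers endpoints and prescribes no sequence; Sections 3 and 9.4.3 name UMSARS-1 first.

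None of this answers the conflict between 2 and 2.5, which is in current text.

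**Conclusion.** The point holds for the margin, the unsourced benchmark and the missing rule. The two stated margins move the futility cut-off by 0.5 point (about 3.5 against 4.0), and the literal reading puts it at about 6.0. This rests on n=38, SD 5.5 and a one-sided 0.05 test, the last assumed from the primary. Of the stated margins, only 2 per subscale agrees with the total's 4.

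The excess over 0.05 is conditional: up to about 0.097 under an either rule with thresholds at 4.5, less where the primary requirement binds, and none if both subscales are required or they are tested in order.

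Two stronger conclusions are not supported. The go/no-go decision for phase 3 is not in doubt on this account: Section 4.1 rests it on the total score alone, so only secondary claims are affected. Nor does margin 2 worsen any stated subscale power, because the plan states none; Section 9.2 sizes the trial on the primary only.

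**What to change.** 1. State one subscale margin in the synopsis, Section 3, Section 9.1 and Section 9.4.3. Two points per subscale fits the total's margin. Add subscale hypotheses to Section 9.1, and say in Section 9.4.3 that the test is against benchmark minus margin, with its sidedness.
2. Give the source of 4.5 (SD 5.5). Where the two sources behind 8.6 report subscale changes, derive the benchmarks from them so that they sum to 8.6. If they do not report them, say so and note that the subscale and total benchmarks come from different data.
3. Put UMSARS-1 and UMSARS-2 on separate steps in a fixed order (the synopsis order is one option), or require both to be significant before MRI is tested.

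The cost is wording in four places and a check of the historical sources, to be done before unblinding. No change to conduct or sample size is needed. The plan should acknowledge that at margin 2 the subscale power is about 0.71 with 38 patients (0.75 with 42), and that 49 would be needed for 0.80. Ordering the subscales or requiring both also makes it harder to reach MRI and OCT than an either rule would.

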4 STUDY DESIGN

4.1 OVERALL DESIGN

To determine whether to test sirolimus in a large phase 3 trial, we propose to conduct a clinical trial of sirolimus in MSA using a futility design. A futility design under the null hypothesis assumes that sirolimus will slow the progression of the disease, whereas the alternative hypothesis assumes no benefit of sirolimus. If the null hypothesis is rejected (i.e., futility of sirolimus to slow progression of MSA), major phase 3 studies will be discouraged, whereas non-futility will offer strong support for a phase III trial to detect clinical efficacy.

To test this hypothesis we will perform a single-center, randomized, double blind, placebo-controlled, phase-II, futility trial, chosen as an efficient approach to determine if sirolimus would be worthy of future investigation in larger, more definite trials. This trial was designed to compare the mean value for the primary outcome measure, change in total Unified Multiple System Atrophy Rating Scale (UMSARS) score from baseline to week 48, between the sirolimus arm and a pre-specified fixed value, representing a 4-point reducing in the expected mean decline without treatment; this fixed value was obtained using data from previously completed a large natural history study(39) and the placebo arm of a recently completed clinical trial in MSA (40). The 4-point reduction was based on the recently reported minimally clinically important decline (MICD) in the total UMSARS score of 3.5-points (38).

The null hypothesis is that sirolimus will reduce the mean decline in the total UMSARS score over 12 month by, at least 4-points, compared with the expected (fixed) value obtained from the historical controls. If the null hypothesis is rejected, then the drug would be considered futile for further investigation in MSA. If the null hypothesis is not rejected, sirolimus would be considered for a phase 3 clinical trial.

Thus, the primary goal is to evaluate the effect of sirolimus on progression of MSA, including autonomic, cerebellar and parkinsonian features as measured by the UMSARS, a relevant clinical measure of disease progression. Secondary goals are to determine if there is any effect on neuroimaging (brain MRI) and ophthalmological (retinal OCT) biomarkers of the disease. As exploratory aim we will determine if there are any changes in plasma α Syn exosomes, as surrogate markers of autophagy.

This study will include a placebo group in 3:1 proportion. Our reason for including a placebo arm is to facilitate blinding to treatment assignment and also to permit a descriptive assessment of the validity of the assumed change in UMSARS over time in the historical control group; the placebo group *will not* be used for primary outcome purposes with the active treatment arm.

This will be single-center study performed at the NYU Dysautonomia Center, one of the leading centers in the diagnosis and management of MSA. [name], the director of the Center, is the PI of the international Natural History Study of MSA, within the NIH-funded Rare Diseases Autonomic Disorders Consortium. NYU has the infrastructure and personnel in place to undertake this study and is experienced in the conduct of clinical trials. NYU is in a position to rapidly commence the study and conduct the study efficiently. We will review the option of adding additional sites if recruitment in the first 15 months is slow. Our aim is to complete recruitment within 24 months from commencement of the study.

Eligible participants, who signed the approved informed consent form at the screening visit, will initially receive sirolimus 2 mg/day (one 2-mg capsule/day) or matching placebo in a 3:1 fashion. The dose of sirolimus will be adjusted throughout the trial based on sirolimus blood levels and the presence of drug-related adverse events. The maximum dose of sirolimus will be 6 mg/day (three 2-mg capsules/day) or matching placebo. Patients receiving placebo will undergo analog sham level measurements and the number of capsules will be also adjusted to maintain the blinding of the trial. Patients will receive active agent or placebo for 48-weeks.

Participants will be evaluated at study clinic by the investigator at the screening visit and at baseline visit and will return to the clinic at Day 84 (month 3), Day 168 (month 6), Day 252 (month 9), and Day 363 (month 12) (+/- 10 days) of beginning the study treatment.

Detailed study plan

Screening visit (Visit -1, Day -42 to -1): Prior to performing any study activities/evaluations, the potential participant must be thoroughly informed about all aspects of the study, including scheduled study visits and activities, and must sign the informed consent. A signed copy of the approved informed consent will be given to the participant. Screening procedures will include demography, medical history, inclusion and exclusion criteria assessment, MSA diagnosis confirmation, physical examination, vital signs & height/weight, EKG, concomitant medication, adverse events, laboratory and safety testing (serum pregnancy test, if applicable, CBC, CMP, CPK, urinalysis and 24-hour urine collection (to quantify the protein/creatinine ratio), lipid panel, HIV, hepatitis B and C serologies, and QuantiFERON®), and UMSARS scale.

COVID-19 nasal swab PCR will be performed at screening. If negative, enroll patient. If positive, patient should be quarantined for at least 2 weeks and consult with their PCP to determine if any treatment is necessary. Participants can be re-screened after 4 weeks with a second nasal swab PCR for COVID-19. If negative, the patient can be enrolled. If still positive, patient will be definitely excluded and recommended continued follow-up with an infectious disease specialist.

If the subject has laboratory tests and EKG results available performed within 90 days before the screening date, it will be allowable to use these for the screening visit.

Safety labs should be performed at least 3 hours after a light (low fat) breakfast.

There will be a screening period of up to 42 days.

Baseline visit (Visit 1, Day 1): The following tasks/procedures will be performed at the clinic during the baseline visit:

- EKG
- MoCA
- Concomitant medications
- Physical examination
- Vitals signs
- CBC, CMP, CPK (8 ml of blood) urinalysis
- Lipid panel
- Dispensing of study medication

- UMSARS scale
- Blood sample for exosomes (2 ml of blood)
- Retinal optical coherence tomography
- 24-hour urine collection. This test should be performed only if the baseline visit occurs > 30 days from the screening visit.

If the baseline visit is performed less than 14 days from the screening visit the following procedures can be foregone, and the results will be assumed to be similar to those obtained at the screening visit:

- EKG
- MoCA
- CBC, CMP, CPK (8 ml of blood), urinalysis
- Lipid panel
- UMSARS scale

Participants will be dispensed study medication during the baseline visit. In case this is not possible, participants will be mailed the study medication within 30 days of the baseline visit.

The case report forms will note the date when the subject will start the study medication.

Participants will also undergo a non-contrast brain MRI with specific sequences to evaluate the diffusion at the putamen and pons. The brain MRI will be performed at the NYU Center for Biomedical Imaging. There will be a brain MRI period of up to 7 days after the baseline visit (i.e., subjects must be scanned within 7 days after the baseline visit).

Scheduled site visits: assessment of the primary outcome measure and safety labs will be conducted on-site at study visits at Visit 8 (month 3 after initiation of study drug), Visit 11 (month 6 after initiation of study drug), Visit 14 (month 9 after initiation of study drug), and Visit 17 (month 12 after initiation of study drug) (+ 15 days). We will accept a visit window of 15 days after the target date. The following tasks will be performed:

- EKG
- Concomitant medications
- Adverse event recording
- Physical exam
- Vital signs
- UMSARS scale
- CBC, CMP, CPK (8 ml of blood) and urinalysis with 24-hour urine collection
- Lipid panel
- Sirolimus levels in blood (5 ml of blood)
- Retrieve study drug
- Dispense study drug. If dispensation of study drug is not possible during the visit, the study drug will be mailed within 15 days.

Safety Laboratory Visits: Assessment of safety will be conducted on-site or locally at study visits 7 days (with a window of 3 days after the target date) after initiation of study drug (Study Visit 3), and 7 days after the patient has increased dose of study drug (i.e., Study Visit 4, Study Visit 5 and Study Visit 6, with

a window of 3 days after the target date) during the first month of study drug treatment. We will accept a visit window of 3 days after the target date of these visits.

Assessment of safety visits will also occur on-site or locally on Month 2 (Study Visit 7, this visit may be skipped in previous visits were delayed, to ensure that Visit 8 occurs at Month 3), Month 4 (Study Visit 9), Month 5 (Study Visit 10), Month 7 (Study Visit 12), Month 8 (Study Visit 13), Month 10 (Study Visit 15), and Month 11 (Study Visit 16). We will accept a visit window of 15 days before or after the target date of these visits.

The following safety laboratory assessments will be performed:

- CBC, CMP, CPK (8 ml of blood) and urinalysis with 24-hour urine collection
- Lipid panel (2 ml of blood)
- Sirolimus levels in blood (5 ml of blood)
- Adverse event reporting

In case the safety lab assessments are performed locally (e.g., at a local laboratory near the subjects' home), the PI or a licensed research member of the team will provide the patient with a prescription for the required tests. A research nurse, investigator or study manager will perform a phone call to assess adverse events within 7 days of the study visit.

To account for delays during the first month of treatment, Visit 7 (2-month) may be skipped to ensure that Visit 8 occurs 3 months (+/- 15 days) after the initiation of the study drug.

To maintain the blinding, the results of the sirolimus levels in blood will remain blinded to the investigators and study coordinators and delivered to the independent pharmacist in charge of determining if the sirolimus dosage should be increased or decreased.

End of study visit/early termination: the following tasks/procedures will be performed at the clinic during the termination visit (Study Visit 17):

- EKG
- MoCA
- Concomitant medications
- Physical examination
- Vitals signs
- CBC, CMP, CPK (8 ml of blood) and urinalysis with 24-hour urine collection
- Lipid panel (2 ml of blood)
- Sirolimus levels in blood (5 ml of blood)
- Retrieve study medication
- Recording of AE
- UMSARS scale
- Blood sample for exosomes (2 ml of blood)
- Retinal optical coherence tomography
- Brain MRI

We will accept a visit window of 15 days before or after the target date of this visit.

The reason for discontinuation of therapy will be documented in the source documents and captured on the CRF. In the event that the study drug is discontinued early, an early termination visit should be

completed as close to the last dose date as possible. Participants will be followed for the duration of 12 months.

If a participant is withdrawn because of an adverse event, the appropriate “Withdrawal Section” of the CRFs should be fully completed in addition to the Adverse Event module. The Independent Medical Monitor should be informed of all participants who are withdrawn for this reason. Participants will be followed for 12 months.

Follow-up phone call: Patients will be contacted 14 days (+/- 5 days) after the End of Study visit to follow up on and record any Aes that were ongoing at the end of their previous visit (Study Visit 18). The follow-up visit may be conducted over the phone; however a response from the patient should be obtained. This response may be obtained by a phone call with the patient and appropriately documented in the source notes. In the event that the patient is unreachable by phone, all reasonable efforts should be made and documented before considering the patient lost to follow-up.

Safety assessment: Assessment of safety will be conducted on-site 30 days (+/- 5 days) after the End of Study visit (Study Visit 19). We accept a visit window of 3 days before or after the target date. The following safety laboratory assessments will be performed:

- CBC, CMP, CPK (8 ml of blood) and urinalysis with 24-hour urine collection
- Lipid panel (2 ml of blood)
- Adverse event reporting

Alternatively, these safety lab assessments can be performed locally (e.g., at a local laboratory near the subjects’ home). In this case, the PI or a licensed research member of the team will provide the patient with a prescription for the required tests. Also, a research nurse or study manager will perform a phone call for adverse event reporting.

Unscheduled visit: An un-scheduled visit may be performed in-office or locally, should the investigators determine the need for so. The following safety laboratory assessments may be performed:

- CBC, CMP, CPK (8 ml of blood) and urinalysis with 24-hour urine collection
- Lipid panel (2 ml of blood)
- Sirolimus levels in blood (5 ml of blood)
- Adverse event reporting

